## **Introduction:**

Within past decades we can observe the clear trend towards the shortening of the hospital stay in patients admitted with the diagnosis of myocardial infarction with ST segment elevations (STEMI).

The current Guidelines of European Society of Cardiology for the management of acute myocardial infarction with ST-segment elevation, released in 2012, state, that in the selected patients may be considered (class of recommendation IIb) early discharge (after approximately 72 hours), if adequate follow-up is arranged.

Level of evidence of cited recommendation is B, i.e. it is based on data, derived from a single randomized clinical trial or large non-randomized studies.

The overview of literature on this topic shows non-uniform methodology of these works and heterogeneous features of studied populations (3 – 63% fulfilled criteria for early discharge!)

In the PAMI II study the low risk was defined as following: age <70 years, left ventricle ejection fraction >45%, one- or two-vessel disease, successful percutaneous coronary intervention (PCI) and no persistent arrhythmias.

In Czech Republic the issue of early discharge was investigated in PRASGUE 5 study (Jirmar et al., 2008), which after pilot phase randomized 56 low risk probands with STEMI, discharged even the next day after successful PCI. The strict inclusion criteria (fulfilled only 3% patients with acute STEMI) included age < 75 years, optimal result of primary PCI, one-vessel disease, left ventricle ejection fraction > 40%, place of residence < 20km, exclusion criteria involved patients after Q-MI, haemodynamically or rhythmically instable, with recurrent chest pain or clinical/laboratory findings requiring additional evaluation.

Followed endpoints were death, reinfarction, stroke, instable angina pectoris, repeat target vessel revascularization, local groin complications requiring treatment and left ventricle ejection fraction within 30 days. This study also showed, that very early discharge in clearly defined group of patients is safe, there was just one rehospitalization due to non-cardiac cause in the group of 37 patients, discharged the next day after MI, there was no other serious event in study population.

By the verification of safety of early discharge this study wants to confirm the applicability of presented conclusions even in the regular clinical practice in our circumstances.

**Design of clinical investigation**

Clinical, prospective, monocentric, randomized, open study

**Study objective:**

The aim of the study is to prove

- that early discharge (within 72 hours) in selected group of patients with low risk of follow-up complications after myocardial infarction with elevations of ST segment, treated with primary percutaneous coronary intervention, is feasible and safe
- that early discharge is „non-inferior“ in comparison with the group of patients, discharged in a standard way accordingly with present practice and physician's decision (usually 4th-7th day), thus it is not associated with higher incidence of complications in 30th and 90th day after myocardial infarction

**Impact on other therapeutic measures:**

The study has no impact on the subsequent care, which is commonly provided to all patients after myocardial infarction: it does not concern the medication, control paraclinical tests and regular clinical controls, scheduled by the attending physician.

**Study population:**

All subjects enrolled in the study.

**Study eligibility:**

All inclusion and no exclusion criteria of enrolled patients must be fulfilled.

**Inclusion criteria:**

- Signed informed consent
- STEMI treated with successful primary PCI within 12 h of the symptom onset (TIMI flow 3 in infarct-related artery)
- Age  $\geq 18$  and  $\leq 75$  years
- Left ventricular ejection fraction  $\geq 45\%$
- One- or two-vessel disease ((stenosis of major epicardial artery  $\geq 70\%$ )
  
- No symptoms of residual ischaemia
- Haemodynamical and rhythmical stability ((Killip class I, no arrhythmia requiring treatment occurring  $> 2$  hours after PCI)
- 
- Absence of comorbidities, requiring continuation of hospitalization
- Absence of contraindication for dual antiplatelet treatment or need for anticoagulation
- Supposed cooperation, adherence to medical measures and social background

**Exclusion criteria:**

- Symptoms of residual ischemia
- Significant comorbidities or abnormalities in paraclinical tests, requiring additional evaluation within continuing hospitalization
- Contraindication of dual antiplatelet therapy or need for anticoagulation therapy
- High risk of bleeding complications
- Participation in other clinical study

**Informed consent:**

All enrolled patients must give their informed consent for participation in the study.

**Endpoints:**

Primary endpoint:

- Composite of incidence of death, reinfarction, unstable angina pectoris, stroke, unplanned rehospitalization, repeat target vessel revascularization and stent thrombosis in 90 days after myocardial infarction

Secondary endpoint:

- Complications associated with the puncture site requiring treatment in 30 days after myocardial infarction

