**Randomization:**

Patients will be assigned into the study groups by the method of simple randomization in ratio 1:1.

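### Both endpoint clocks start at the infarction while the time of randomisation is left open, so events before randomisation count as outcomes, chiefly for the puncture-site endpoint

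*Combined protocol and SAP*

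**What the plan says.** Under Endpoints, the primary composite closes with "repeat target vessel revascularization and stent thrombosis in 90 days after myocardial infarction", and the secondary endpoint is "Complications associated with the puncture site requiring treatment in 30 days after myocardial infarction". Both clocks therefore start at the index infarction.

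The Randomization section is one sentence: "Patients will be assigned into the study groups by the method of simple randomization in ratio 1:1". It does not say when, relative to PCI or to the discharge decision, this happens.

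Several entry criteria depend on what is seen after PCI. They include TIMI 3 flow, "no arrhythmia requiring treatment occurring" more than 2 hours after PCI, "No symptoms of residual ischaemia" and "Absence of comorbidities, requiring continuation of hospitalization". Exclusion criteria adds "Significant comorbidities or abnormalities in paraclinical tests, requiring additional evaluation within continuing hospitalization". None has a time of assessment or a closing time.

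Study objective compares discharge within 72 hours with usual practice, typically day 4 to 7, and claims non-inferiority without a margin. Statistic plans Fisher's exact test at p < 0.05. No section says how events before randomisation are handled.

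**The concern.** Start of follow-up, confirmation of eligibility and allocation should coincide, or their order should be stated. Here follow-up starts first, eligibility is settled some time after PCI, and allocation floats. Anything that happens between the infarction and randomisation falls inside the outcome window, although allocation has not yet occurred and discharge timing cannot have caused it.

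The plainest case is a puncture-site complication treated on day 1 in a patient randomised on day 2. Applied literally, the secondary endpoint counts it. Such events carry no information about early discharge and make the arms look more alike on a ratio scale. That is awkward in a trial that hopes to show no excess of complications and has no margin against which to judge it.

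**Working it through.** **Step 1: which events can precede randomisation in an enrolled patient?**

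- Death: impossible.
- Unplanned rehospitalisation: impossible before discharge.
- Reinfarction, unstable angina, symptomatic stent thrombosis, stroke: would normally breach the criteria on residual ischaemia, stability, or findings that need further inpatient work-up.
- Repeat target-vessel procedure: possible if early and resolved, and if the investigator still judges the patient low-risk and in no need of further inpatient evaluation. Probably uncommon.
- Treated puncture-site complication: no criterion specifically excludes it. The exclusions for high bleeding risk and for findings needing continued stay may remove some patients.

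**Step 2: effect on the secondary endpoint.** The documents give no rates, so all inputs are assumed: later risks of 1% (standard) and 2% (early discharge), and a share c in each arm with an event before randomisation. Taking early and later events as occurring in different patients, the counted rates are c + 1% and c + 2%.

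| c | Standard | Early discharge | Ratio | Difference |
|---|---|---|---|---|
| 0% | 1% | 2% | 2.00 | 1 point |
| 2% | 3% | 4% | 1.33 | 1 point |
| 4% | 5% | 6% | 1.20 | 1 point |
| 10% | 11% | 12% | 1.09 | 1 point |

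If early and later events are independent and each patient counts once, the counted rate is c + (1 − c) × later rate. At c = 4% this gives 4.96% and 5.92%, a ratio of 1.19 and a difference of 0.96 points. The difference shrinks only by the factor (1 − c).

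**Step 3: effect on the planned test.** The planned enrolment of 150 to 200 cannot be reproduced, because no event rate, effect, margin or power is given. With the stated 2% loss, 150 × 0.98 / 2 = 73.5 (taken as 74) or 200 × 0.98 / 2 = 98 patients per arm remain. Assumed later rates are 5% and 15%, chosen only to show the mechanism for a binary endpoint. Counted rate = c + (1 − c) × later rate, and power is by exact enumeration of the two-sided Fisher test at 0.05.

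| c | Counted rates | Ratio | Difference (points) | Power, 98 per arm | Power, 74 per arm |
|---|---|---|---|---|---|
| 0% | 5.0% v 15.0% | 3.00 | 10.0 | 57% | 44% |
| 2% | 6.9% v 16.7% | 2.42 | 9.8 | 49% | 37% |
| 5% | 9.75% v 19.25% | 1.97 | 9.5 | 40% | 30% |
| 10% | 14.5% v 23.5% | 1.62 | 9.0 | 30% | 22% |

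**Step 4: effect on an interval for the absolute difference.** With equal later rates of 5% and 98 per arm, the 95% half-width is 1.96 × √(2q(1 − q)/98), where q = c + (1 − c) × 5%. It is 6.1 points at c = 0 and 7.1, 8.3 and 9.9 points at c = 2%, 5% and 10%. Against a margin on the risk difference, the extra events would make non-inferiority harder to show.

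**Step 5: net direction for the primary composite.** Unplanned rehospitalisation can run the other way. A problem on day 4 to 7 may be a readmission in the early arm but inpatient care in the standard arm. Time at risk of readmission to day 90 is 90 − 3 = 87 days after discharge on day 3, against 90 − 7 = 83 to 90 − 4 = 86 days after standard discharge.

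**The case against.** The infarction clock matches the stated objective, which refers to days 30 and 90 after the infarction, and the entry criteria already screen out most early primary events. Both points are right, and they confine the problem mainly to the secondary endpoint. The Introduction also suggests that early events are few: in the Czech trial of next-day discharge, with 56 randomised low-risk patients, it reports one non-cardiac rehospitalisation and no other serious event. That trial was small and more tightly selected, so it does not show that c is zero.

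Three stronger readings are tempting, and the documents do not support them.

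- *A reader might infer that the primary comparison is biased towards no difference.* The ratio and the power of Fisher's test do shrink, but the absolute difference barely moves, its interval widens, and rehospitalisation can count against early discharge. Shared early events are also equal only in expectation, not in number.
- *A reader might infer that counting inpatient events after randomisation, while both arms are still in hospital, is an error.* It is the ordinary comparison of groups as randomised, and counting from randomisation would still include those events.
- *A reader might infer that the rule "All inclusion and no exclusion criteria of enrolled patients must be fulfilled" permits removal of patients after allocation.* It is an entry requirement. Study population takes everyone enrolled, the section on ending the study mentions only the patient's own withdrawal as a way to end participation, and Statistic restricts the analysis to those who complete follow-up, not to those who remain eligible. For the same reason, residual ischaemia as an entry criterion does not clash with unstable angina as an outcome.

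**Conclusion.** The concern holds in a limited form. As written, events before randomisation count as outcomes. The exposure is clearest for puncture-site complications and narrow for the primary composite.

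On the secondary endpoint, with the assumed 1% versus 2% later risks, 4% of earlier events turn a ratio of 2.0 into 1.2 and leave a difference of about 1 point. The true size is unknown, because the documents give no early event rate and no time of randomisation. If patients are randomised very soon after PCI, little precedes allocation and the problem is small.

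The dilution favours the trial's claim only if a non-significant Fisher result is read as non-inferiority. The plan leaves that open by stating no margin, but that is a separate weakness. The net direction for the primary composite is uncertain. Severity is moderate and confidence is moderate.

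**What to change.** **Randomization.** State the point at which patients are randomised: after every inclusion and exclusion criterion has been confirmed and time-stamped, and before the allocation is revealed. State that eligibility is fixed at that point.

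**Endpoints.** Count the primary and secondary endpoints from randomisation. The end dates of day 90 and day 30 after the infarction may stay, in line with the objective. Record earlier events, puncture-site complications in particular, as baseline data by arm.

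**Optional.** Add a sensitivity analysis that starts at a common, pre-specified landmark time in both arms, to address shared inpatient events after randomisation. The landmark should not fall after early-arm discharges have begun, or events that discharge could have influenced would be dropped.

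**Cost.** Wording in two sections and one eligibility time stamp on the case report form. Slightly fewer events will be counted.

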**Definitions:****Myocardial infarction**

Criteria for the acute myocardial infarction (MI):

evidence of myocardial necrosis in a clinical setting consistent with acute myocardial ischaemia.

Under these conditions any one of the following criteria meets the diagnosis for MI:

- Detection of a rise and/or fall of cardiac biomarker values [preferably cardiac troponin (cTn)] with at least one value above the 99th percentile upper reference limit (URL) and with at least one of the following:
  - Symptoms of ischaemia.
  - New or presumed new significant ST-segment–T wave (ST–T) changes or new left bundle branch block (LBBB).
  - Development of pathological Q waves in the ECG.
  - Imaging evidence of new loss of viable myocardium or new regional wall motion abnormality.
  - Identification of an intracoronary thrombus by angiography or autopsy.
- Cardiac death with symptoms suggestive of myocardial ischaemia and presumed new ischaemic ECG changes or new LBBB, but death occurred before cardiac biomarkers were obtained, or before cardiac biomarker values would be increased.
- Percutaneous coronary intervention (PCI) related MI is arbitrarily defined by elevation of cTn values ( $>5 \times$  99th percentile URL) in patients with normal

baseline values ( $\leq$ 99th percentile URL) or a rise of cTn values  $>20\%$  if the baseline values are elevated and are stable or falling. In addition, either (i) symptoms suggestive of myocardial ischaemia or (ii) new ischaemic ECG changes or (iii) angiographic findings consistent with a procedural complication or (iv) imaging demonstration of new loss of viable myocardium or new regional wall motion abnormality are required.

- Stent thrombosis associated with MI when detected by coronary angiography or autopsy in the setting of myocardial ischaemia and with a rise and/or fall of cardiac biomarker values with at least one value above the 99th percentile URL.
- Coronary artery bypass grafting (CABG) related MI is arbitrarily defined by elevation of cardiac biomarker values ( $>10 \times$  99th percentile URL) in patients with normal baseline cTn values ( $\leq$ 99th percentile URL). In addition, either (i) new pathological Q waves or new LBBB, or (ii) angiographic documented new graft or new native coronary artery occlusion, or (iii) imaging evidence of new loss of viable myocardium or new regional wall motion abnormality.

#### Criteria for prior myocardial infarction

Any one of the following criteria meets the diagnosis for prior MI:

- Pathological Q waves with or without symptoms in the absence of non-ischaemic causes.
- Imaging evidence of a region of loss of viable myocardium that is thinned and fails to contract, in the absence of a non-ischaemic cause.
- Pathological findings of a prior MI.

#### ST-segment elevation – ECG characteristics

New ST elevation at the J point in two contiguous leads with the cut-points:  $\geq 0.1$  mV in all leads other than leads V2–V3 where the following cut points apply:  $\geq 0.2$  mV in men  $\geq 40$  years;  $\geq 0.25$  mV in men  $< 40$  years, or  $\geq 0.15$  mV in women.

#### Percutaneous coronary intervention

Refers to all interventional cardiology methods for treatment coronary artery disease

#### Unstable angina

is considered to be present in patients with ischemic symptoms suggestive of an ACS and no elevation in troponin, with or without ECG changes indicative of ischemia (eg, ST segment depression or transient elevation or new T wave inversion).

#### Stroke

Presence of focal neurological deficit, occurring due to brain vessel lesion, persisting > 24 hours or lasting < 24 hours, if the pharmacological or non-pharmacological treatment was applied

Target vessel revascularization

Any repeat percutaneous intervention or surgical bypass of any segment of target vessel

Stent thrombosis:

Definite

The presence of an angiographic confirmation of stent thrombosis (the presence of a thrombus that originates in the stent or in the segment 5 mm proximal or distal to the stent) is associated with the presence of at least one of the following criteria within a 48-hour window: acute onset of ischaemic symptoms at rest, new ischaemic electrocardiographic changes that suggest acute ischaemia or typical rise and fall in cardiac biomarkers; or in the presence of a pathological confirmation of stent thrombosis (evidence of recent thrombus within the stent determined at autopsy or via examination of tissue retrieved following thrombectomy). The incidental angiographic documentation of stent occlusion in the absence of clinical signs or symptoms is not considered a confirmed stent thrombosis (silent occlusion).

Probable

Probable stent thrombosis is defined as the presence of any unexplained death within the first 30 days after stent implantation, or in the presence of any MI related to documented acute ischaemia in the territory of the implanted stent without angiographic confirmation of stent thrombosis and in the absence of any other obvious cause, irrespective of the time after the index procedure.

Possible

Possible stent thrombosis is defined as any unexplained death from 30 days after intracoronary stenting until the end of follow-up.

TIMI (Thrombolysis In Myocardial Infarction) classification:

developed by TIMI study group to semiquantitatively assess coronary artery perfusion beyond point of occlusion on coronary angiography.

TIMI 3 – complete perfusion: normal flow with complete filling of the distal territory

[figure not shown]
Serious adverse event

Any adverse drug experience occurring at any dose that results in any of the following outcomes:

- Life-threatening
- Death
- Hospitalization/prolongation of hospitalization
- Congenital anomaly
- Persistent or significant disability/incapacity
- Required intervention to prevent permanent impairment/damage

## Other adverse events

Adverse events that are not Serious adverse events

**Plan of study:**

**Number of probands:**

Enrollment of about 150-200 patients is planned

**Expected total duration of clinical investigation:**

3 years

**Randomization:**

Patients will be assigned into the study groups by the method of simple randomization in ratio 1:1.

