**Statistic:**

All subjects, participating in the study and completing the follow-up, will be involved into the statistical analysis. Considered rate of probands lost within follow-up is 2%.

The adequate methods of statistical evaluation of the study results will be used. Baseline demographic, clinical, angiographic, periprocedural data and results will be summarized using descriptive summary statistics.

Fischer's exact test will be used for comparison of qualitative variables between two groups. For comparison of quantitative variables Mann-Whitney U test, respectively Student's t-test will be used. Normality of data will be assessed with Shapiro-Wilk test. The value  $p < 0.05$  will be considered as statistically significant.

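### The primary comparison is only an unstratified Fisher's exact test, which gives no estimate or interval for the non-inferiority aim and ignores one- versus two-vessel disease

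*Combined protocol and SAP*

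**What the plan says.** - **Objective.** The Study objective section aims to prove that early discharge is non-inferior to standard discharge. No margin, expected event rate or power is given.
- **Design.** "Clinical, prospective, monocentric, randomized, open study".
- **Allocation.** "Patients will be assigned into the study groups by the method of simple randomization in ratio 1:1". No blocks, strata or concealment procedure are described.
- **Size.** "Enrollment of about 150-200 patients is planned".
- **Population.** The Inclusion criteria admit "One- or two-vessel disease". Vessel number is an entry criterion, so it is known from the angiogram before allocation.
- **Endpoint.** The primary endpoint is a composite at 90 days, which each patient either has or does not have.
- **Analysis.** "Fischer's exact test will be used for comparison of qualitative variables between two groups". A p-value below 0.05 "will be considered as statistically significant"; sidedness is not stated. Results are also to be summarised descriptively. No risk difference, confidence interval, stratification or covariate adjustment is named.

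**The concern.** Two gaps meet in the Statistic section.

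First, Fisher's exact test addresses whether the arms differ. Non-inferiority asks how much worse early discharge could be, and that needs an estimated difference with an interval. In a small trial of low-risk patients, a non-significant Fisher test is likely whether or not early discharge is acceptably safe.

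Second, the trial enrols one- and two-vessel patients together, and neither the allocation nor the analysis takes account of this. If a visible imbalance arises, the only adjustment available would be chosen after seeing the data. In a trial with few events, that invites doubt about the result.

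**Working it through.** **Inputs from the documents:** total N of 150 to 200, 1:1 simple randomization, a binary primary endpoint, and both vessel groups eligible. **Assumed, because the documents give none:** 30-40% two-vessel disease (35% in step 3), the event rates shown, and a two-sided 95% interval. The planned N has no stated derivation, so there is no figure of the plan's own to reproduce.

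**Step 1: what the Fisher test leaves unsaid.** Take equal arms and the same event rate p in both. The standard error of the risk difference is √[4p(1−p)/N].
- N=150, p=5%: √(4×0.05×0.95/150) = 0.0356. The 95% half-width is 1.96×0.0356 = 7.0 points.
- N=200, p=5%: √(4×0.05×0.95/200) = 0.0308. The half-width is 6.0 points.

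With identical observed rates the Fisher test shows no difference, yet excesses of up to 6-7 points are not excluded. Only the interval reveals this.

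**Step 2: how much is left to chance.** Arm size follows Binomial(N, 0.5).
- The central 95% range of one arm is 63-87 (N=150) or 86-114 (N=200).
- A gap of 20 or more between arms has probability 12.1% (N=150) or 17.9% (N=200).
- The between-arm difference in two-vessel share has SD of about 2√[q(1−q)/N]. At q=40% this is 0.080 (N=150) or 0.069 (N=200).
- For q of 30-40%, a difference of 10 points or more has probability of about 18-21% (N=150) or 12-15% (N=200).
- Within one period of 25-33 patients, a 60:40 or worse split has probability of about 22-42% (42% at 25 patients, 22% at 32).

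**Step 3: precision gained by stratifying the analysis, simple randomization kept.** With stratum rates r₁ and r₂, two-vessel share q = 0.35 and overall rate p = 0.65r₁ + 0.35r₂, the share of variance lying between strata is q(1−q)(r₂−r₁)² / [p(1−p)]. The last column gives the reduction found by simulating the Mantel-Haenszel risk difference against the crude one at N=150.

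| r₁ v r₂ | p | Between-stratum / total | Share | Simulated |
|---|---|---|---|---|
| 5% v 5% | 0.0500 | 0 / 0.0475 | 0% | about 0% |
| 5% v 12% | 0.0745 | 0.00111 / 0.0689 | 1.6% | about 1% |
| 4% v 16% | 0.0820 | 0.00328 / 0.0753 | 4.4% | about 4% |
| 3% v 20% | 0.0895 | 0.00657 / 0.0815 | 8.1% | about 8% |

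The simulated figures are slightly lower because estimating within strata costs a little when the arms are unbalanced.

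**Step 4: size of a chance shift.** The 95% limit for the shift in the crude risk difference is 1.96 × SD of the share × (r₂−r₁). At N=150, q=0.35 and 5% v 12%, this is 1.96×0.0779×0.07 = 1.1 points, against a standard error of √(4×0.0689/150) = 4.3 points.

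**Step 5: what blocks would add and cost.** With random blocks of 4 or 6 within the two vessel strata (35% two-vessel), simulation gives:
- The 95th percentile of the arm-size gap falls from 24 to 2 (N=150) or from 28 to 2 (N=200).
- The 95th percentile of the difference in two-vessel share falls from 15.3 to 1.8 points or from 13.3 to 1.3 points.
- The SD of the risk difference hardly moves: 0.0514 to 0.0500 at N=150 with 8% v 16%, and unchanged at 0.0354 with 5% in both strata.
- Someone who knows past assignments guesses the next one correctly about 69% of the time, or about 68% with blocks of 4, 6 or 8. Under simple randomization the figure is 50%.

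**The case against.** The strongest reply is that simple randomization is not an error. It is unbiased, and chance imbalance is already covered by the test's error rate. Mean efficiency is 99.3% (N=150) or 99.5% (N=200) of that with equal arms. At the edge of the 95% range, non-inferiority power falls by about 1 point or less, for example from 79.4% to 78.4% at N=150 with an assumed 5% rate and 10-point margin. This stands, and it is why the point concerns the analysis and not the allocation.

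It is also true that the documents give no event rates by vessel number. The Introduction reports one earlier trial that placed one- and two-vessel disease in a single low-risk class, and another that took one-vessel disease only. The larger gains in the table need a four- to nearly sevenfold contrast in event rates. This stands too: the precision argument is weak and rests on assumptions.

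The authors could point to the general promise of adequate methods and to the descriptive summary of results. Event percentages by arm would let a reader subtract, but neither statement commits the trial to an estimate, an interval or a stratification factor. This part does not answer the point.

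A reader might infer three stronger things that the documents do not support:
- **That simple randomization should be replaced by blocks at almost no cost.** The trial is open and single-centre, past assignments are visible, and eligibility includes a judgement of expected cooperation. Added predictability is a real price, and competent statisticians differ on the trade.
- **That blocks would guard against drift in usual length of stay.** The Introduction does mention a "clear trend towards the shortening of the hospital stay", but over past decades. Drift in the comparator dilutes the contrast under any allocation method. The three years stated are also the total duration of the investigation, not the recruitment period.
- **That baseline variables will be significance-tested.** The Statistic section plans descriptive summaries for baseline data and never says that they will be tested.

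**Conclusion.** The point holds for the analysis. An unstratified Fisher p-value cannot support the stated non-inferiority aim, and a stratified risk difference with interval is a better primary analysis at no real cost. The main gain is an estimate and interval that address the objective, with a pre-specified adjustment in place of a post hoc one. The precision gain is secondary: about 0% of variance if event rates do not differ by vessel number, and about 1-8% at N=150 for 5% v 12% to 3% v 20%, all with 35% two-vessel disease assumed. Simple randomization is valid and may stay. The missing non-inferiority margin is a separate and more serious gap: without it, the interval has nothing to be judged against.

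**What to change.** **Statistic section (recommended).** State that the primary comparison of the 90-day composite is the Mantel-Haenszel risk difference (early minus standard discharge) with its confidence interval, stratified by one- versus two-vessel disease. State the confidence level and name an interval method suited to few events. Fisher's exact test may remain as a supporting analysis. The cost is about two sentences of text: the factor is already established at entry, and no extra patients, visits or data are needed.

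**Randomization section (optional).** If the investigators also want balance by design, use permuted blocks of randomly varying size, stratified by vessel number. Keep block sizes undisclosed, have the list held by someone who does not enrol patients, and reveal each assignment only after eligibility and consent are recorded. This would largely reduce chance imbalance, not remove it, at the price of more predictable allocation. If simple randomization is kept, the analysis change works unaltered.
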